Patients **in both arms** who tolerate axitinib for at least two consecutive weeks with no adverse reactions $>$ Grade 1 considered clinically significant (according to the Common Toxicity Criteria for Adverse Events [CTCAE]), will, at the discretion of their treating physician, have the axitinib dose increased to 7 mg twice daily beginning on **cycle 2 day 1**, unless the patient's blood pressure is $>$ 150/90 or the patient is receiving more than one antihypertensive medication. Subsequently, with the same criteria, patients who tolerate the axitinib dose of 7 mg twice daily for at least two consecutive weeks may have the axitinib dose increased to a maximum of 10 mg twice daily beginning with **cycle 3 day 1**. Dose reductions of axitinib and TRC105 are allowed per patient tolerance. Each cycle is 28 days.

Number of patients (planned):

Approximately 30 patients with advanced renal cell carcinoma will be enrolled in the phase 1b portion and approximately 150 patients with advanced or metastatic renal cell carcinoma will be enrolled in the phase 2 portion.

Diagnosis and main criteria for inclusion:**Inclusion Criteria:**

1. **PHASE 2 ONLY:** Histologically confirmed advanced or metastatic renal cell carcinoma with a clear cell component that has progressed by investigator assessment on treatment with one and only one multi-targeted tyrosine kinase inhibitor (TKI) other than axitinib that targets the VEGF receptor (VEGFR) (e.g., sunitinib, pazopanib, sorafenib, tivozanib, cabozantinib) **OR** bevacizumab. Patients who received VEGF inhibitor treatment for \leq one month due to documented intolerance in the absence of progression, and were started on a second VEGF inhibitor within one month of discontinuing the initial VEGF inhibitor are eligible. One prior immunotherapy (interleukin-2 or interferon-alpha or immune checkpoint inhibitor or tumor vaccine) and one prior mTOR inhibitor treatment are allowed. Prior adjuvant therapy is permitted in the absence of disease progression during treatment, but no further VEGF treatment is allowed if progression occurred on adjuvant VEGF inhibitor treatment.

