11. **TRC105 Administration:** Intravenous TRC105 diluted in normal saline will be administered every 7 days. The first weekly TRC105 dose (cycle 1 day 1) will split into two doses whereby 3 mg/kg is administered on cycle 1 day 1 and 7 mg/kg is administered on cycle 1 day 4. The entire weekly dose of TRC105 (10 mg/kg) is then given on cycle 1 day 8 and weekly thereafter. See Section 6.1.6 for specific TRC105 administration guidelines.
12. **Axitinib Dosing:** Oral axitinib will be dosed twice daily on days 1-28 of each 28 day cycle according to the axitinib package insert. Patients who tolerate the starting dose with no adverse reactions above grade 2 for four weeks will have the axitinib dose increased. See Section 6.2 for specific dosing guidelines.
13. **Imaging:** CT or MRI scans of chest, abdomen, and pelvis with contrast to be performed at screening, and on-study as outlined in the assessment table. If subjects are unable to receive CT contrast due to CT contrast medium allergy or renal insufficiency, enhanced MRI scans may be used. A

combination of non-contrast CT and MRI studies (such as chest CT without contrast and abdominal MRI with contrast) may be used. The same method of assessment must be used throughout the course of the study thereafter. Similarly, if a subject develops a contraindication to CT contrast during the course of the study; assessments may shift to non-contrast CT of the chest and contrast-enhanced MRI of the abdomen for subsequent scans. In addition, a brain MRI or CT with contrast to be performed at screening to assure absence of CNS metastases and on study as needed if metastases are suspected. Bone scans are to be performed at screening and throughout the study at the time of CT assessments if bone metastases are present and cannot be followed by CT. Known areas of disease should be consistently followed throughout the study. Assessments should be performed whenever disease progression is suspected. Allowable window for tumor imaging studies is +/- 7 days. Scans will be performed every 56 days from date of randomization.

14. **12-Lead ECG:** Single tracing 12-lead ECG will be performed at screening and at time points indicated in the Schedule of Assessments (pre-dose). For a QTc >500 ms, a repeat ECG for confirmation and evaluation of the ECG by a cardiologist is recommended. Additional ECGs may be performed on study as clinically indicated.

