7. No major surgical procedure or significant traumatic injury within 6 weeks prior to study registration, and must have fully recovered from any such procedure; date of surgery (if applicable). Note: the following are not considered to be major procedures and are permitted up to 7 days before therapy initiation: Thoracentesis, paracentesis, port placement, laparoscopy, thoracoscopy, tube thoracostomy, bronchoscopy, endoscopic ultrasonographic procedures, mediastinoscopy, skin biopsies, incisional biopsies, imaging-guided biopsy for diagnostic purposes, and routine dental procedures
8. Uncontrolled chronic hypertension defined as systolic $>$ 150 or diastolic $>$ 90 despite optimal therapy (initiation or adjustment of BP medication prior to study entry is allowed provided that the average of 3 BP readings at a visit prior to enrollment is $<$ 150/90 mm Hg)

9. History of brain involvement with cancer, spinal cord compression, or carcinomatous meningitis, or new evidence of brain or leptomeningeal disease. Patients with radiated or resected lesions are permitted, provided the lesions are fully treated and inactive, patients are asymptomatic, and no steroids have been administered for at least 28 days.
10. Angina, MI, symptomatic congestive heart failure, cerebrovascular accident, transient ischemic attack, arterial embolism, pulmonary embolism, PTCA or CABG within the past 6 months. Deep venous thrombosis within 6 months unless the patient is anticoagulated without the use of warfarin for at least 2 weeks. In this situation, low molecular weight heparin is preferred.
11. Active bleeding or pathologic condition that carries a high risk of bleeding (e.g. hereditary hemorrhagic telangiectasia).
12. Thrombolytic use (except to maintain i.v. catheters) within 10 days prior to first day of study therapy
13. Known active viral or nonviral hepatitis or cirrhosis
14. History of hemorrhage or hemoptysis (> ½ teaspoon bright red blood) within 3 months of starting study treatment
15. History of peptic ulcer disease within 3 months of treatment, unless treated for the condition and complete resolution has been documented by esophagogastroduodenoscopy (EGD) within 28 days of starting study treatment
16. History of gastrointestinal perforation or fistula in the past 6 months, or while previously on antiangiogenic therapy, unless underlying risk has been resolved (e.g., through surgical resection or repair)

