6.2.6. Axitinib Dose Modification

Patients who are intolerant of axitinib may continue TRC105 treatment alone on the study.

Axitinib should be held for two weeks prior and for two weeks following surgical procedures.

Dose reduction is allowed based on individual safety and tolerability. Following dose interruption, axitinib treatment may be reinitiated when the toxicity that prompted dose reduction has resolved to baseline or grade 1. See axitinib package insert in [Section 20.3](#).

All patients will initially receive axitinib 5 mg twice daily; patients randomized to receive TRC105 will receive TRC105 at 3 mg/kg on day 1, 7 mg/kg on day 4, and 10 mg/kg on day 8 and weekly thereafter. Patients **in both arms** who tolerate axitinib for at least two consecutive weeks with no adverse reactions > Grade 1 considered clinically significant (according to the Common Toxicity Criteria for Adverse Events [CTCAE]), will, at the discretion of their treating physician, have the axitinib dose increased to 7 mg twice daily beginning on cycle 2 day 1, unless the patient's blood pressure is > 150/90 or the patient is receiving more than one antihypertensive medication. Subsequently, with the same criteria, patients who tolerate the axitinib dose of 7 mg twice daily for at least two consecutive weeks may have the axitinib dose increased to a maximum of 10 mg twice daily beginning with cycle 3 day 1. Dose reductions of axitinib and TRC105 are allowed per patient tolerance (including to doses of axitinib between 5 and 10 mg twice daily). Reasons for dose reduction and reasons for not increasing the axitinib dose will be documented on the CRF.

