Over the course of treatment, management of some adverse drug reactions may require temporary interruption or permanent discontinuation and/or dose reduction of axitinib therapy (including hypertension and hypertensive crisis, arterial and venous thromboembolic events, hemorrhage, gastrointestinal perforation and fistula formation, thyroid dysfunction, reversible posterior leukoencephalopathy syndrome, wound healing complications, proteinuria, and liver enzyme elevations). If dose reduction from 10 mg twice daily is required the recommended dose is 7 mg twice daily. If dose reduction from 7 mg twice daily is required, the recommended dose is 5 mg twice daily. If dose reduction from 5 mg twice daily is required, the recommended dose is 3 mg twice daily. If additional dose reduction is required, the recommended dose is 2 mg twice daily.

In the case of persistent hypertension despite use of anti-hypertensive medications, reduce the axitinib dose. Discontinue axitinib if hypertension is severe and persistent despite anti-hypertensive therapy and dose reduction of axitinib, and discontinuation should be considered if there is evidence of hypertensive crisis. If axitinib is interrupted, patients receiving antihypertensive medications should be monitored for hypotension.

Axitinib should be discontinued in patients who develop arterial thrombosis and the patient should be removed from study. Patients with grade 1 or 2 venous thromboembolism may dose reduce and continue treatment if it is the wish of the patient and physician and if the anticoagulation guidelines specified in [Section 6.3](#) are satisfied.

Axitinib should be interrupted for any bleeding requires medical intervention, gastrointestinal perforation, fistula, reversible posterior leukoencephalopathy syndrome, or surgical procedure. Interruption prior to and following surgery should be for a minimum of 2 weeks.

Thyroid function should be monitored before initiation of, and periodically throughout, treatment with axitinib. Treat hypothyroidism and hyperthyroidism according to standard medical practice to maintain a euthyroid state.

The dose of axitinib should be temporarily interrupted and/or reduced for patients who develop grade 3 or 4 proteinuria or grade 3 or 4 transaminase or bilirubin elevations.

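### The axitinib footnotes to Tables 9–11 escalate patients whom Section 6.2.6 does not allow to escalate, and omit its blood-pressure and antihypertensive limit

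*Protocol*

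**What the plan says.** The axitinib dosing footnote in all three phase 2 schedules (Protocol Table 9 footnote 11 for Arm A, Table 10 footnote 12 for Arm B weekly, Table 11 footnote 12 for Arm B every two weeks) contains the sentence "Patients who tolerate the starting dose with no adverse reactions above grade 2 for four weeks will have the axitinib dose increased". It names no target dose and then refers the reader to Section 6.2. The same sentence is in footnote 12 of phase 1b Tables 7 and 8.

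Section 6.2.6 gives the fuller rule, for both arms. The patient must tolerate axitinib for "at least two consecutive weeks with no adverse reactions > Grade 1 considered clinically significant". Such patients will then, "at the discretion of their treating physician, have the axitinib dose increased to 7 mg twice daily", starting on cycle 2 day 1. The exception is a patient whose "blood pressure is > 150/90 or the patient is receiving more than one antihypertensive medication". The Synopsis and Section 4.1.1.2 state the same rule with the same limit.

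Three other provisions bear on the point:
- Section 6.2.6 says of documentation that "reasons for not increasing the axitinib dose will be documented on the CRF".
- Section 6.2.6 also instructs: "In the case of persistent hypertension despite use of anti-hypertensive medications, reduce the axitinib dose".
- Exclusion criterion 8 (Section 5.1.2) sets blood-pressure thresholds for entry and notes that "initiation or adjustment of BP medication prior to study entry is allowed". It sets no limit on the number of antihypertensives.

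**The concern.** The schedule tables are operative text. Section 4.1.2.2 has its listed procedures carried out according to the Schedule of Assessments, and axitinib dosing is one of them. A site working from the table therefore has a dosing instruction with a toxicity criterion, a duration and an action, but without the blood-pressure and antihypertensive limit.

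A site following it could raise axitinib in a patient whom Section 6.2.6 keeps at 5 mg twice daily. Section 2.3.6.1 lists hypertension among the most common axitinib reactions and hypertensive crisis among the rare but significant ones, so the omitted limit guards against a risk that the protocol itself names.

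The conflict also blurs compliance. The same dose increase can follow the table and breach Section 6.2.6. Protocol deviations are captured (Protocol Section 12) and tabulated by treatment group (SAP Section 19.3).

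**Working it through.** No sample size, power or alpha figure is involved. The check sets the two rules side by side and then applies each to the same patients.

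**The rules**

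| Element | Footnotes, Tables 9–11 | Section 6.2.6 (also Synopsis and 4.1.1.2) |
|---|---|---|
| Toxicity ceiling | Grade 2 | Grade 1, for clinically significant reactions |
| Duration | Four weeks | At least two consecutive weeks |
| Obligation | Dose will be increased | Treating physician's discretion |
| Blood-pressure limit | None | No increase if > 150/90 |
| Antihypertensive limit | None | No increase if on more than one |
| Target dose | None given | 7 mg twice daily |

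**Applied to patients at the end of cycle 1**

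| Patient | Footnote | Section 6.2.6 |
|---|---|---|
| A. Two antihypertensives, BP below 150/90, no reaction at all | Increase | Barred |
| B. BP > 150/90, no reaction above grade 2 | Increase | Barred |
| C. Clinically significant grade 2 reaction, no clean two-week run | Increase | Not allowed |
| D. Grade 3 reaction in week 1, then at least two weeks with nothing clinically significant above grade 1; BP and antihypertensive limits met | No increase | Can increase |

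Patient A can be enrolled, because exclusion 8 limits blood pressure and not the number of drugs. The case does not depend on how hypertension is graded. Patient B does depend on it: how many patients above 150/90 stay at or below grade 2 is a matter for CTCAE, which the protocol only links (Appendix 1). Patient D shows that the mismatch also runs the other way. Types A to C can overlap and are not a count.

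**Dose step at stake**

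- 5 mg × 2 = 10 mg/day
- 7 mg × 2 = 14 mg/day
- (14 − 10) / 10 = +40%

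The footnote concerns only the starting dose, so the later step from 7 to 10 mg twice daily is not in conflict.

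**Where each rule stands**

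- Footnote sentence: 3 phase 2 tables (9, 10, 11), or 5 tables with phase 1b (7, 8).
- Full rule: 3 places (Synopsis, 4.1.1.2, 6.2.6).

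**The case against.** The strongest reply is that the footnote cannot be carried out alone. It gives no target dose and sends the reader to Section 6.2. Each narrative statement of the increase to 7 mg (Synopsis, 4.1.1.2, 6.2.6) carries the blood-pressure limit in the same sentence. Only Table 17 gives the dose without it; that table is headed as an ideal schedule and sits inside 6.2.6. On this view the footnote is a loose summary and the intended rule is not in doubt. This lowers the risk. But the footnote already states a criterion, a duration and an action, and does not say that Section 6.2 prevails. A reader who follows the pointer finds a contradictory rule rather than further detail.

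Other points, and what stands of them:
- **Timing.** Four weeks against two matters little for the date of the increase, since both rules lead to cycle 2 day 1. This stands, but grade, discretion and the blood-pressure and antihypertensive limit still differ.
- **Documentation.** Blood pressure is measured at scheduled visits, and reasons for not increasing go on the CRF. That field records non-escalation, so it would not flag a wrongful increase. Blood-pressure and concomitant-medication records could show one, but after exposure.
- **Phase 1b experience.** Patients reached 7 and 10 mg twice daily without dose-limiting toxicity (Section 2.3.4.1). That is some reassurance. However, the DLT window for cohorts 1 and 2 was cycle 1 (Section 4.1.1.1), and the same safety section reports grade 1–3 hypertension.
- **Phase 1b tables.** Section 6.2.6 speaks of both arms, and phase 1b has none. This stands: for Tables 7 and 8 the rule needs confirming, and no conflict is asserted.
- **Table 11.** It cannot be used until the sponsor gives notice. True, but the same sentence is in Tables 9 and 10.

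**Conclusion.** The concern holds. Read literally, the footnotes to Tables 9–11 direct a dose increase in patients whom Section 6.2.6 does not allow to escalate, and they omit its blood-pressure and antihypertensive limit. The two-antihypertensive patient with a clean cycle 1 is enough to show this and needs no assumption about grading.

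The size in dose terms is one step of +40%. The size in patients is unknown, because the documents do not give the share on two or more antihypertensives or the share above 150/90 with no reaction above grade 2. The wording is the same in both arms, so no bias between arms is claimed. The three consistent statements of the full rule and the pointer to Section 6.2 make this a conflict that should be corrected, not one that threatens the trial's conclusions.

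**What to change.** In Tables 9, 10 and 11, do one of the following:

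1. Replace the sentence with the Section 6.2.6 criteria: two consecutive weeks, no clinically significant reaction above Grade 1, physician discretion, and no increase if BP is > 150/90 or the patient is on more than one antihypertensive.
2. Delete the sentence and keep only the reference to Section 6.2.

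Confirm the intended phase 1b escalation rule, then align the same sentence in Tables 7 and 8.

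The cost is one footnote sentence in three phase 2 tables, and in two phase 1b tables once that rule is confirmed. Data collection, sample size and analysis do not change.

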5. SELECTION AND WITHDRAWAL OF PATIENTS

5.1. Patient Inclusion Criteria

5.1.1. Inclusion Criteria:

1. **PHASE 2 ONLY:** Histologically confirmed advanced or metastatic renal cell carcinoma with a clear cell component that has progressed by investigator assessment on treatment with one and only one multi-targeted tyrosine kinase inhibitor (TKI) other than axitinib that targets the VEGF receptor (VEGFR) (e.g., sunitinib, pazopanib, sorafenib, tivozanib, cabozantinib) **OR** bevacizumab. Patients who received VEGF inhibitor treatment for < one month due to documented intolerance in the absence of progression, and were started on a second VEGF inhibitor within one month of discontinuing the initial VEGF inhibitor are eligible. One prior immunotherapy (interleukin-2 or interferon-alpha or immune checkpoint inhibitor or tumor vaccine) and one prior mTOR inhibitor treatment are allowed. Prior adjuvant therapy is permitted in the absence of disease progression during treatment, but no further VEGF treatment is allowed if progression occurred on adjuvant VEGF inhibitor treatment.
2. **PHASE 1B COHORT 3 AND 4 ONLY:** Histologically confirmed advanced or metastatic renal cell carcinoma that has progressed by investigator assessment on treatment with at least **TWO** VEGF inhibitors (e.g., sunitinib, pazopanib, sorafenib, tivozanib, cabozantinib, bevacizumab). Prior immunotherapy (interleukin-2 or interferon-alpha or immune checkpoint inhibitor or tumor vaccine), or mTOR inhibitor treatment is allowed.
3. No other prior malignancy is allowed except for the following: adequately treated basal cell or squamous cell skin cancer, adequately treated Stage I or II cancer from which the patient is currently in complete remission per investigators' clinical judgment.
4. Measurable disease by RECIST 1.1 criteria
5. Age of 18 years or older
6. ECOG performance status ≤ 1
7. Resolution of all acute adverse events resulting from prior cancer therapies to NCI CTCAE grade ≤ 1 or baseline (except alopecia)
8. Adequate organ function as defined by the following criteria:
 - AST and ALT $\leq 2.5 \times$ ULN **OR** $\leq 5 \times$ ULN in cases of liver metastases
 - Total serum bilirubin ≤ 1.5 times the upper limit of normal
 - Absolute neutrophil count (ANC) $\geq 1500/\mu\text{L}$
 - Platelets $\geq 100,000/\mu\text{L}$ without transfusion support within the past 28 days
 - Hemoglobin ≥ 9.0 g/dL without transfusion support within the past 14 days (erythropoietin or darbepoetin permitted)

-
- Serum creatinine \leq 1.5 times the upper limit of normal or creatinine clearance $>$ 30 mL/min by Cockcroft-Gault formula
 - INR between 0.8 – 1.2
9. Willingness and ability to consent for self to participate in study
 10. Willingness and ability to comply with scheduled visits, treatment plan, laboratory tests, and other study procedures
 11. Men who are sterile (including vasectomy confirmed by post vasectomy semen analysis) OR agree to use a condom with spermicide (refer to [Section 2.3.6.1](#)) and to not donate sperm during the study and for at least 180 days following last dose of TRC105 or axitinib.
 12. Woman of non-child bearing potential due to surgical sterilization (at least 6 weeks following surgical bilateral oophorectomy with or without hysterectomy or tubal ligation) confirmed by medical history or menopause (i.e., no menstrual bleeding for more than 12 months in a woman aged 45 years or more), OR woman of child bearing potential who test negative for pregnancy at time of enrollment based on serum pregnancy test and agree to use at least two acceptable methods of birth control, one of which must be highly effective (refer to [Section 2.3.6.1](#)) during the study and for at least 180 days after stopping TRC105 or axitinib (refer to [Section 2.3.6.1](#)).

5.1.2. Exclusion Criteria:

1. **PHASE 2 ONLY**: Prior treatment with TRC105 or axitinib or any agent targeting the endoglin pathway (including a fusion protein that binds bone morphogenic protein)
2. **PHASE 1B COHORT 3 AND 4 ONLY**: Prior treatment with TRC105
3. Grade 3 or 4 toxicity related to prior VEGF inhibitor that did not resolve to grade 1
4. Current treatment on another therapeutic clinical trial
5. Receipt of systemic anticancer therapy, including investigational agents, within 28 days of starting study treatment. If anticancer therapy was given within 28 days of starting study treatment, patients may be included if 5 times the elimination half-life of the drug passed.
6. Prior radiation therapy within 28 days of starting the study treatment, except radiation therapy for bone metastases or radiosurgery is permitted up to 14 days of starting treatment
7. No major surgical procedure or significant traumatic injury within 6 weeks prior to study registration, and must have fully recovered from any such procedure; date of surgery (if applicable). Note: the following are not considered to be major procedures and are permitted up to 7 days before therapy initiation: Thoracentesis, paracentesis, port placement, laparoscopy, thoracoscopy, tube thoracostomy, bronchoscopy, endoscopic ultrasonographic procedures, mediastinoscopy, skin biopsies, incisional biopsies, imaging-guided biopsy for diagnostic purposes, and routine dental procedures
8. Uncontrolled chronic hypertension defined as systolic $>$ 150 or diastolic $>$ 90 despite optimal therapy (initiation or adjustment of BP medication prior to study entry is allowed provided that the average of 3 BP readings at a visit prior to enrollment is $<$ 150/90 mm Hg)

9. History of brain involvement with cancer, spinal cord compression, or carcinomatous meningitis, or new evidence of brain or leptomeningeal disease. Patients with radiated or resected lesions are permitted, provided the lesions are fully treated and inactive, patients are asymptomatic, and no steroids have been administered for at least 28 days.
10. Angina, MI, symptomatic congestive heart failure, cerebrovascular accident, transient ischemic attack, arterial embolism, pulmonary embolism, PTCA or CABG within the past 6 months. Deep venous thrombosis within 6 months unless the patient is anticoagulated without the use of warfarin for at least 2 weeks. In this situation, low molecular weight heparin is preferred.
11. Active bleeding or pathologic condition that carries a high risk of bleeding (e.g. hereditary hemorrhagic telangiectasia).
12. Thrombolytic use (except to maintain i.v. catheters) within 10 days prior to first day of study therapy
13. Known active viral or nonviral hepatitis or cirrhosis
14. History of hemorrhage or hemoptysis (> ½ teaspoon bright red blood) within 3 months of starting study treatment
15. History of peptic ulcer disease within 3 months of treatment, unless treated for the condition and complete resolution has been documented by esophagogastroduodenoscopy (EGD) within 28 days of starting study treatment
16. History of gastrointestinal perforation or fistula in the past 6 months, or while previously on antiangiogenic therapy, unless underlying risk has been resolved (e.g., through surgical resection or repair)
17. Known human immunodeficiency virus (HIV) or acquired immunodeficiency syndrome (AIDS) related illness
18. Receipt of a strong CYP3A4/5 inducer within 12 days prior to cycle 1 day 1 or a strong CYP3A4/5 inhibitor within 7 days prior to cycle 1 day 1 (refer [Table 18](#)).
19. Other severe acute or chronic medical (including bone marrow suppressive diseases) or psychiatric condition or laboratory abnormality that may increase the risk associated with study participation or may interfere with the interpretation of study results and, in the judgment of the Investigator, would make the patient inappropriate for this study
20. Patients with known hypersensitivity to Chinese hamster ovary products or other recombinant human, chimeric, or humanized antibodies.
21. Significant ascites or pericardial or pleural effusion
22. Patients with hereditary problems of galactose intolerance, including Lapp lactase deficiency or glucose-galactose malabsorption

